### • Recurrence of Disease (RD)

Relapse after CR is defined as a reappearance of leukemic blasts in the peripheral blood or  $\geq 5\%$  blasts in the bone marrow aspirate not attributable to any other cause or reappearance or new appearance of extramedullary leukemia. Relapse after PR is similarly defined with reappearance of significant numbers of peripheral blasts and an increase in the percentage of blasts in the bone marrow aspirate to > 25% not attributable to any other cause or reappearance or new appearance of extramedullary leukemia.

Best Response measurement: Response will be measured and defined for primary endpoints as the best response achieved during the first 3 cycles of therapy, or at time off study, for those subjects discontinuing treatment before the completion of 3 cycles of therapy. Best response is defined to be the best-measured response (ORR=CR+CRp+PR+MLFS) post-treatment up to that time. Best response will also be evaluated for the full treatment period using all assessments up to and including treatment discontinuation.

**Duration of Response**: length of time from the first objective evidence of response to the first objective evidence of disease progression.

**Progression-Free Survival**: length of time (up to 5 years) from the date of first treatment to the first objective evidence of disease progression or death, whichever is earlier.

**Overall Survival**: length of time from the date of first administration of study drug to the date of death from any cause.

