## Phase 1 Study of IACS-010759 in Subjects with relapsed or refractory AML

#### Study Synopsis and Objectives

This is an open label Phase 1 study of IACS-10579 utilizing a 3+3 dose-escalation phase followed by an expansion phase in subjects with relapsed or refractory AML and no available treatment options with known benefit.

In cohorts 1 and 2, in the first cycle, IACS-010759 will be administered on Day 1 followed by continuous dosing starting on day 8 through day 28; cycles 2 and beyond will be continuous daily dosing. Based on PK analysis and modeling of preliminary data from cohorts 1 and 2, the study design has been amended. In cohort 3 and subsequent cohorts, in the first cycle, IACS-010759 will be administered daily for up to 7 days during an initial Induction Phase (Day 1-7) followed the Maintenance Phase (Day 8-21), which will use a lower dose to maintain steady state drug levels. For cohort 3, the maintenance dose will be administered once weekly on Day 8 and Day 15 of the 21-day cycle in cycle 1; in subsequent cycles, doses will be administered on Days 1, 8 and 15 of each cycle, unless alternate schedules are recommended by the SMC. In subsequent cohorts, the induction and maintenance doses and/or the dosing interval during the maintenance phase may be further modified by the SMC based on safety, PK and PD data observed. Dosing will continue until confirmed progressive disease, initiation of alternative cancer therapy, unacceptable toxicity, or other reasons to discontinue treatment prematurely at the dose levels given below:

Original Dose Escalation Regimen, Cohorts 1 and 2:

PHASE	COHORT	NO OF SUBJECTS	IACS-010759 DOSE LEVEL (DAILY EXCEPT CYCLE 1, DAY 2-7) *
Dose-	Cohort 1	3-6	0.5 mg
escalation	Cohort 2	3-6	1 mg

\*Intermediate doses of IACS-010759, not to exceed 8 mg, not listed above may also be pursued with SMC approval depending on the safety, PK and PD data observed.

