#### 4.1.15 Follow-Up at Treatment Discontinuation or Early Withdrawal

Subjects who discontinue treatment for any reason should complete end-of-treatment procedures when possible. End of treatment procedures will include a physical examination, CBC with differential and platelets and chemistry. A bone marrow aspiration may be recommended only if non-response or progressive disease cannot be unequivocally diagnosed from peripheral blood. Although treatment will be discontinued at that time, all subjects who do not die, withdraw consent for follow-up, or become lost to follow-up, will remain on study for

follow-up evaluations. Subject will be followed for possible delayed emergence of IACS-010759 related toxicity at least 30 days after the last protocol treatment. Subjects who discontinue the study will be requested to return for additional PK and/or PD blood daws, approximately every 4 days, when possible, for up to 4 weeks after the last study drug administration to further explore the PK and PD activity of IACS-010759 following discontinuation of study drug. The 30-day (+/-7 days) follow-up visit will be scheduled as a clinic visit for clinical evaluation and physical examinations. If the subject cannot make it to the site for this visit, the required follow up treatment procedures may be performed by a local physician and the records forwarded to the site. The research nurse will also contact the subject by telephone and obtain a verbal assessment of the subject's condition. The phone conversation will then be documented in the subject's charts.

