Study Day	-7 to -1	1+	2	4	5*	8	12	15	17	21	22	29	36	37	42	43	63	Every 2	L days	30 after last Dose
Name of Cycle Day		C1 D1	C1 D2	C1 D4	C1 D5	C1 D8	C1 D12	C1 D15	C1 D17	C1 D21	C2 D1	C2 D8	C2 D15	C2 D16	C2 D21	C3 D1	C3 D21	CX D20	CX D21	51
+/- days allowable				1			1	1	2	+2	1	1	1	2	1	3	3	4	4	7
Study Drug§		II	NDUC	CTION	J P							MA	INTEN	ANCE P						
Disease Assessment																				
Bone marrow aspirate and/or biopsy¥	Х									Х							х	Every 2-3 cycle		Х
Overall Response Rate ‡										Х							Х		X ‡	Х
Study Procedures & Examinations																				
Eligibility Assessment & Informed Consent	Х																			
Demographics A	Х																			
Medical history B	Х																			
MUGA/ECHO	Х																			
Dilated eye exam with fundus photos N		Х																		
Neurology review and exam o		Х																		
12-lead ECG (QTcF)	Х	X 			X 			X 		Х										
Phys. Exam (inc. weight)	Х	Х			Х			Х		Х	Х				Х	Х	Х		Х	Х
ECOG	Х	Х									Х					Х			Х	Х
Vital Signs (Temp., HR, BP, RR)	Х	X 	X 	X 	X 	X 	Х	X 		Х	X 	X 	X 	Х	Х	X 	Х		Х	Х
Concomitant Medication C	Х	Х	Х	Х	Х	Х	Х	Х	Х	Х	Х	Х	Х	Х	Х	Х	Х		Х	Х
Adverse Events D		Х	Х	Х	Х	Х	Х	Х	Х	Х	Х	Х	Х	Х	Х	Х	Х		Х	Х
Labs																				
Pregnancy test	Х																			
Blood Hematology E, I, J	Х	X 			X 	X 	Х	X 	Χ	Х	Х			Х	Х	Х	Х		Х	Х
Chemistry F, I	Х	X 			X 	X 	Х	X 	Χ	Х	Х	X 	X 	Х	Х	Х	Х		Х	Х
Coagulation, lipase, amylase & urinalysis G, I	Х	X 			X 	X 	Х	X 	Х	Х	Х	X 	X 	Х	Х				Х	Х
Lactate and blood pH I, K	Х	X 	X 	X 	X 	X 	Х	X 	Χ	Х	X 	X 	X 	Х	Х	X 	Х		Х	Х
Research Labs																				
Blood collection- pharmacodynamics H	Х	X 			X 			X 		Х										Χ L

Research Bone marrow aspirate/or biopsy	X									Х									

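### For subjects who stop before 3 cycles, best response is read at an undefined time off study with no cut at new anti-leukemic therapy, so a response to the next regimen can count for IACS-010759

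*Combined protocol and SAP*

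**What the plan says.** Section 4.4.2 (Best Response measurement) gives two windows.

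- **3-cycle window.** Best response over the first 3 cycles, "or at time off study, for those subjects discontinuing treatment before the completion of 3 cycles of therapy". What counts is the best measured response "post-treatment up to that time".
- **Full-period window.** "Best response will also be evaluated for the full treatment period using all assessments up to and including treatment discontinuation".

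Three other places bear on when these windows close.

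- Section 4.1.15: after treatment stops, "all subjects who do not die, withdraw consent for follow-up, or become lost to follow-up, will remain on study for" follow-up evaluations. It adds: "The 30-day (+/-7 days) follow-up visit will be scheduled as a clinic visit for clinical evaluation and physical examinations".
- Section 4.2: each flowchart marks both the bone marrow and the Overall Response Rate row in the End of Study or Early Termination column, timed at "30 after last Dose" with a 7-day allowance.
- Synopsis (and 4.1.6): dosing runs until confirmed progression, "initiation of alternative cancer therapy, unacceptable toxicity, or other reasons to discontinue treatment prematurely".

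**The concern.** In 4.1.15 and the flowcharts, leaving the study comes later than leaving treatment. If off study in 4.4.2 means what it means there, a subject who stops early has a best-response window that runs past the last dose into a period when another regimen may have begun. Nothing in 4.4.1 or 4.4.2 excludes an assessment made after that point. A longer best-response window can only add responders, so any error favors the study drug.

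The two definitions also fail to nest. The full treatment period should contain the first 3 cycles, yet for an early stopper the 3-cycle window can close later.

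Overall response rate is a secondary endpoint, and 4.1.7 lists response data among the inputs to the RP2D. A misattributed response in an escalation cohort could therefore enter that judgement.

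**Working it through.** The plan states no figure that rests on this definition. Section 4.1.5 says the 18 expansion subjects do not come from a formal calculation, so there is nothing to reproduce. The check is of wording, timing and the weight of one response.

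**1. What off study means.** Section 4.4.2 uses time off study in one sentence and treatment discontinuation in a later sentence of the same paragraph. Two terms so close together suggest two times. Section 4.1.15 agrees, since it separates stopping treatment from leaving the study. Against this, 4.1.13 speaks of subjects who came off study because of a DLT, where stopping treatment appears to be meant. The later time is the natural reading but not the only one.

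**2. Whether anything cuts response at new therapy.** Sections 4.4.1 and 4.4.2 contain no such rule. Section 5.1 criterion 9 and section 7.1 item 5 bar other cancer therapy during the study, with exceptions. Neither says that starting it ends participation or closes the response window. The synopsis and 4.1.6 treat its start as a reason to end dosing.

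**3. Timing, cohorts 3-7.** Let L be the study day of the last dose. The End of Study reading falls at L + 30, with a range of L + 23 to L + 37. Cycle 3 ends on Day 63.

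| Last dose (L) | End of Study reading | Range |
|---|---|---|
| Day 21 | Day 51 | 44 to 58 |
| Day 42 | Day 72 | 65 to 79 |

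If treatment discontinuation is taken as the last dose, the early stopper's 3-cycle window outlasts the full-period window by 23 to 37 days. It passes the Day 63 close used for completers when L is later than 63 − 30 = Day 33 (Day 26 to Day 40 across the visit allowance).

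Section 4.4.1 schedules disease assessment at the end of Cycles 1 and 3. A subject who stops between those two visits has End of Study as the only scheduled response assessment after Cycle 1.

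**4. Weight of one response.** One response adds 1/18 = 5.6 points in the expansion set, or 1/6 = 16.7 points in a full escalation cohort. Exact 95% intervals, the type named in 4.4.1, are:

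| Responders | Rate | Exact 95% CI |
|---|---|---|
| 0/18 | 0% | 0 to 18.5 |
| 1/18 | 5.6% | 0.1 to 27.3 |
| 2/18 | 11.1% | 1.4 to 34.7 |
| 0/6 | 0% | 0 to 45.9 |
| 1/6 | 16.7% | 0.4 to 64.1 |

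**5. How many such responses to expect.** This would need three fractions: subjects stopping before 3 cycles, those of them starting new therapy before the End of Study assessment, and those of them responding by then. The documents give neither of the first two. The 10-30% in 2.1 is a general salvage response rate in relapsed AML, not a rate within about 30 days in subjects who have also stopped this drug. No estimate follows.

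**The case against.** The strongest answer is that off study simply means off treatment. The phrase is attached to subjects discontinuing treatment, and 4.1.13 uses it that way. On that reading both the misattribution and the conflict between the windows disappear. There is also tension in stretching study to cover follow-up for the response window while limiting the bars on other therapy, which apply during the study, to the treatment period. Both points stand as evidence of ambiguity. They do not settle the meaning, and the contrast with treatment discontinuation in the same paragraph points the other way.

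Section 4.1.15 also narrows the exposure. Its end-of-treatment procedures are an examination, blood counts and chemistry, with a marrow recommended only when non-response or progression is not clear from peripheral blood. CR, CRi, PR and MLFS all rest on marrow, so many clear failures will have no late marrow, despite the flowchart mark. That stands and makes misattribution less frequent.

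Three stronger readings are tempting but unsupported.

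- *The window is open-ended.* The scheduled reading is 23 to 37 days after the last dose.
- *The rate could be inflated by up to 11 points.* Assume 9 of 18 stop early, 25-75% of them start new therapy in time and 10-30% respond. That gives 9 × 0.25 × 0.10 = 0.225 to 9 × 0.75 × 0.30 = 2.03 responders, or 1.3 to 11.3 points of 18. The first two inputs have no source. Enrolled subjects have no remaining options of known benefit and are not candidates for standard therapy or transplant at enrollment (5.1), so the upper end is not credible.
- *Expansion responses distort the RP2D.* Under 4.1.8 expansion subjects receive an RP2D already chosen, so only escalation-phase responses can inform it.

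Finally, 4.4.2 already has a version closed at treatment discontinuation, and the objectives section defers detail to a SAP finalized before database lock. That gives a place for the correction; it does not correct the 3-cycle rule as written.

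**Conclusion.** The point holds as a defect in a stated endpoint rule. On the natural reading of 4.4.2 with 4.1.15 and the flowcharts, a response seen after the next regimen has started can count for IACS-010759, and a subject can respond within 3 cycles yet not within the full treatment period. The other reading of off study cannot be excluded, which is itself a reason to define the term.

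The direction is known: if it occurs, the response rate is overstated. The frequency is not known and is probably low. What can be said is the weight of each case, 5.6 points in 18 subjects or 16.7 in 6. Response is a secondary, descriptive endpoint with no decision threshold, although 4.4.2 calls it primary in passing. No sample size or error rate changes. The correction is worth making because it is cheap and the error runs one way.

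**What to change.** In 4.4.2 and the SAP, replace the undefined cut-off with one end-point rule for both best-response definitions. Only disease assessments made before the start of any new anti-leukemic therapy, including transplant, and no later than the End of Study visit should count. The 3-cycle window still closes at cycle 3 for subjects who complete 3 cycles. For early stoppers both windows then end together, so the shorter always lies within the longer. Subjects with no qualifying assessment stay in the denominator as non-responders.

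Start dates of new therapy can come from the concomitant medication record, which the flowcharts already collect with start and end dates through End of Study. Because that record is laid out for drugs, check that it also captures a transplant.

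The cost is protocol and SAP wording. The reported 3-cycle rate may be slightly lower. The full-period rate may gain an occasional response seen after the last dose but before any new therapy. Whether to censor progression-free survival and duration of response at new therapy is a separate choice on which statisticians may differ, and it is not part of this recommendation.

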### 4.5 IACS-010759 Plasma Drug Levels

#### 4.5.1 Subject Evaluation & Statistics

Only subjects who received at least one dose of IACS-010759, and provided both the baseline sample and at least one post-treatment sample, will be evaluated.

### 4.5.2 Endpoints & Assessment Methods

Collection of samples to assess the plasma concentration of IACS-010759 will be required for all subjects. Peripheral blood (5 mL) will be collected at the time points indicated in section 4.2.

A validated LC-MS/MS bioanalytical method will be used at the MDACC, Institute for Applied Cancer Science (IACS) research labs, located at [name] to quantify IACS-010759 in human plasma.

Pharmacokinetic parameters will be calculated using Phoenix WinNonlin 6.3 software package.

### 4.6 Biological activity of IACS-010759

### 4.6.1 Subject Evaluation & Statistics

Only subjects who received at least one dose of IACS-010759, and provided the baseline and at least one post-treatment sample, will be evaluated.

PD data will be summarized graphically and with descriptive statistics by time and dose.

### 4.6.2 Endpoints & Assessment Methods

To evaluate PD biomarkers, approximately 30 cc of peripheral blood will be collected in green top tubes and 5 cc of bone marrow will be collected at the time points indicated in section 4.2. Upon isolation of blasts cells, baseline and post-treatment biological activity will be assessed using assays that are informed by preclinical studies using AML cell line and subject derived models. These include but are not limited to:

- Pre and post-treatment measurement of OXPHOS inhibition, using Seahorse Seahorse
   XF bioanalyzer to measure oxygen consumption in blast cells isolated from the peripheral blood.
- Pre and post-treatment measurement of metabolites related to mitochondria metabolism, glycolysis, amino acid and nucleotide biosynthesis, to measure changes that have been associated with inhibition of OXPHOS and response in preclinical models.
- Pre and post treatment measurement of mRNAs using gene expression profiling or other quantitative methods to assess mRNA signatures that has been identified utilizing preclinical models treated with IACS-010759.

Any leftover sample or tissue including bone marrow, if available, will be stored for potential future exploratory research into factors that may influence development of AML and/or response to IACS-010759 (where response is defined broadly to include efficacy, tolerability or safety) or additional exploratory pharmacogenetic evaluations, including RNA microarray analyses or DNA, and xenografting into immunodeficient mice. Excess samples will be stored at MD Anderson Cancer Center, IACS laboratory, located at [name].

# 5 Subject Eligibility

#### 5.1 Inclusion Criteria

Eligible subjects **must fulfill** all of the following criteria:

1. Subjects with AML should have failed any prior induction therapy regimen or have relapsed after prior therapy (defined as patients in first relapse and less than 12 months from diagnosis [short first remission] or in second or later relapse

Dose-escalation phase: Subjects with confirmed relapsed or refractory AML and no available treatment options with known benefit

Expansion phase: Subjects with relapsed/refractory AML who have failed therapy with up to one prior salvage regimen and no available treatment options with known benefit Exception: stem cell transplant [SCT] or stem cell therapy for subjects who previously underwent SCT/stem cell therapy, and are currently in remission will not be considered a salvage regimen.

- 2. Eastern Cooperative Oncology Group (ECOG) ≤ 2 (see appendix 9.3)
- 3. Patients who have had prior SCT are eligible if they have a relapse > 3 months since autologous or allogeneic stem cell transplantation provided,
  - No clinically significant active graft-versus-host disease (GVHD > grade 1).
  - No treatment with high dose steroids for GVHD (i.e. >20 mg Prednisolone or equivalent per day).
  - No treatment with immunosuppressive drugs with the exception of cyclosporine and tacrolimus.
- 4. Subjects with history of CNS disease are allowed if at the time of day 1 of the study there is no evidence of active CNS disease as documented by negative imaging or spinal fluid analysis carried out at least 2 weeks prior to the first study drug administration in a subject with no clinical signs of CNS disease.
- 5. Adequate renal and hepatic function:
  - Serum creatinine ≤ 2.0 X ULN
  - Total bilirubin  $\leq$  2 times the upper limit of normal (ULN) (or </=3.0 x ULN if deemed to be elevated due to Gilbert's disease or leukemia)
  - ALT and AST ≤ 2.5 times ULN (≤ 5.0 x ULN if due to leukemic involvement).
- 6. Negative urine pregnancy test within 72 hours prior to the first dose of study therapy for women of child-bearing potential (WCBP), defined as a sexually mature woman who has not undergone a hysterectomy or who has not been naturally post-menopausal for at least 24 consecutive months (i.e., who has had menses any time in the preceding 24 consecutive months).
- 7. Have been informed of other treatment options and is not a candidate for standard treatment options or stem cell transplant at the time of enrollment.
- 8. Age  $\geq$ 18 years.
- 9. In the absence of rapidly progressing disease, the interval from prior treatment to time of initiation of IACS-010759 administration will be at least 2 weeks or 5 half-lives (whichever is shorter) for cytotoxic/noncytotoxic agents and biological/immune-based therapies, including investigational agents. The half-life for the therapy in question will be based on published pharmacokinetic literature (abstracts, manuscripts, investigator brochures, or drug-administration manuals) and will be documented in the protocol eligibility document. The use of chemotherapeutic or anti-leukemic agents is not permitted during the study with the following exceptions: (1) intrathecal (IT) therapy for subjects with controlled CNS leukemia at the discretion of the PI and with the agreement of the Sponsor. (2) Use of hydroxyurea for subjects with rapidly proliferative disease is allowed before the start of study therapy and for the first 2 cycles on therapy. These medications will be recorded in the case-report form.

10. Women of childbearing potential must agree to use an adequate method of contraception during the study and until 3 months after the last treatment. Males must be surgically or biologically sterile or agree to use an adequate method of contraception during the study until 3 months after the last treatment.

Adequate methods of contraception include:

- Total abstinence when this is in line with the preferred and usual lifestyle of the subject. Periodic abstinence (e.g., calendar, ovulation, symptothermal, post-ovulation methods) and withdrawal are not acceptable methods of contraception.
- Female sterilization (have had surgical bilateral oophorectomy with or without hysterectomy) or tubal ligation at least six weeks before taking study treatment. In case of oophorectomy alone, only when the reproductive status of the woman has been confirmed by follow up hormone level assessment
- Male sterilization (at least 6 months prior to screening). For female subjects on the study, the vasectomized male partner should be the sole partner for that subject
- Combination of any of the two following (a+b or a+c or b+c)
- Use of oral, injected or implanted hormonal methods of contraception or other forms of hormonal contraception that have comparable efficacy (failure rate <1%), for example hormone vaginal ring or transdermal hormone contraception
- b. Placement of an intrauterine device (IUD) or intrauterine system (IUS)
- c. Barrier methods of contraception: Condom or Occlusive cap (diaphragm or cervical/vault caps) with spermicidal foam/gel/film/cream/ vaginal suppository In case of use of oral contraception, women should have been stable on the same pill before taking study treatment.

**Note:** Oral contraceptives are allowed but should be used in conjunction with a barrier method of contraception due to unknown effect of drug-drug interaction. Women are considered postmenopausal and not of child bearing potential if they have had 12 months of natural (spontaneous) amenorrhea with an appropriate clinical profile (e.g. age appropriate, history of vasomotor symptoms) or have had surgical bilateral oophorectomy (with or without hysterectomy) or tubal ligation at least six weeks ago. In the case of oophorectomy alone, only when the reproductive status of the woman has been confirmed by follow up hormone level assessment is she considered not of child bearing potential.

11. Able and willing to give valid written informed consent.

